### **6.2. Efficacy Assessments**

#### **6.2.1. Daily Migraine Assessment by Severity**

Participants will be asked to submit electronic records every day after receiving the eDiary device including whether migraine occurred, whether migraine was associated with aura, the duration of the headache, symptoms, pain features, use of migraine-specific medications (study medication, triptan, or ergotamine), as well as severity of the headache. A qualified migraine day will be identified using the eDiary data based on the definition in [Appendix 2](#) Section [12.2](#). The number of migraine days will then be calculated by total and intensity of the migraine headache.

### **6.3. Urine Drug Screening**

A urine drug screen will be performed at the Screening Visit to exclude drug abusers.

## **6.4. Serum Virology Testing**

Serum virological examination will be performed at Screening Visit, including HBsAg, HCV antibody test, HIV antibody test. HbsAb, HbeAg, HbeAb, HbcAb, and HBV DNA quantification will be conducted If HBsAg is positive.

## **6.5. Other Assessments**

### **6.5.1. Migraine Quality of Life Questionnaire**

The MSQoLQ version 2.1 will be used to assess the impact of treatment on participants' quality of life. The MSQoLQ has 14 items that have been validated in migraineurs to measure the impact of treatment (within past 4 weeks of the questionnaire) on migraine-specific domains: work, social function, energy, vitality, feelings, concerns, and migraine symptoms .

### **6.5.2. Migraine Preference of Medicine**

The PoM is a brief scale that captures participants' perception of whether the study medication they are taking has a greater benefit compared with previous medications to treat their pain. BYOD will be used to evaluate the Preference of Medication Scale.

### **6.5.3. Satisfaction with Medication Questionnaire**

The Satisfaction with Medication Questionnaire is a brief rating scale that captures participants' perceptions of whether they are satisfied with the medication for migraine. BYOD will be used to evaluate the Satisfaction with Medication Questionnaire.

### **6.5.4. Migraine Disability Assessment Questionnaire (MIDAS)**

The Migraine Disability Assessment Questionnaire is a retrospective participant self-reported rating scale of 5 questions measuring the time lost in headache-related disabilities such as headaches due to paid work or school, housework, and nonwork activities. The MIDAS will be completed on paper forms at the site .

### **6.5.5. Clinical Global Impression-Change (CGI-c)**

The CGI-c scale is a brief, observer-rated assessment that rates participant total improvement relative to the investigator's past experience with other participants with the same diagnosis, with or without collateral information .

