##### **3.1.3. Exploratory Objectives**

- To evaluate the effect of 75 mg rimegepant ODT treatment compared to baseline on the 14-Item MSQoLQ version 2.1.
- To evaluate the effect of 75 mg rimegepant ODT treatment on the PoM.
- To evaluate the effect of 75 mg rimegepant ODT treatment on the Satisfaction with Medication survey.
- To evaluate the effect of 75 mg rimegepant ODT treatment compared to baseline on the MIDAS.
- To evaluate the effect of 75 mg rimegepant ODT treatment on the CGI-c scale.

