### 3.2.3. Exploratory Endpoints

- Change from baseline in results assessed with the 14-item MSQoLQ version 2.1 following treatment with 75 mg rimegepant ODT;
- Percentage of participants in each of 3 preference categories of the assessment with Migraine PoM for migraine following treatment with 75 mg rimegepant ODT;
- Percentage of participants in each of 7 satisfaction categories of the Satisfaction with Medication survey following treatment with 75 mg rimegepant ODT;
- Change from baseline in total score of the MIDAS following treatment with 75 mg rimegepant ODT;
- Percentage of participants in each of 7 categories of the CGI-c scale after treatment with 75 mg rimegepant ODT.

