- Return unused study drug for compliance check (at each site visit);
- Return eDiary and review eDiary and BYOD of completion for completeness (at each site visit);

- Daily recording of migraine attacks and their severity by eDiary;
- MSQoLQ Version 2.1 (at Weeks 12, 28, 40, 52, or early termination);
- Migraine PoM for migraine (Week 28 and Week 52 or at early termination);
- Satisfaction with Medication survey (Week 28 and Week 52 or Early Termination);
- CGI-c scale (at Weeks 28 and 52 or early termination);
- MIDAS (at Weeks 12, 28, 40, 52 or early termination).

Upon completion of the Baseline Visit, WOCBP will be provided with urinary pregnancy test kits so that participants can test at home if necessary. When WOCBP participants cannot confirm pregnancy status, a urine pregnancy test must be completed at home before taking study drugs.

During the treatment period, participants have to use the last bottle of study drug before opening a new bottle of study drug. Three wallets of study drug will be dispensed to the participants at each visit of Week 4, Week 8, and Week 12. Study drug will be dispensed at Week 16, Week 28, Week 40 visits as needed, the maximum dispensing limit for each visit is 7 bottles per participant. Study drug will be dispensed at site visits as needed. Dispensing of study drug may also occur at unscheduled visits as needed.

If a participant lacks 6 or more diary reports per month for 2 months (continuous or non-continuous), the participant's continued participation in the study should be terminated due to lack of compliance.

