2.3 Exploratory Objectives

- To evaluate the effect of 75 mg Rimegepant ODT treatment compared to baseline on the 14-Item Migraine-Specific Quality of Life Questionnaire v 2.1 (MSQoLQ).
- To evaluate the effect of 75 mg Rimegepant ODT treatment on the Migraine Preference of Medication (PoM).
- To evaluate the effect of 75 mg Rimegepant ODT treatment on the Satisfaction with Medication (SM) survey.
- To evaluate the effect of 75 mg Rimegepant ODT treatment compared to baseline on the Migraine Disability Assessment (MIDAS).
- To evaluate the effect of 75 mg Rimegepant ODT treatment on the Clinical Global Impression-change (CGI-c) scale.

3 Study Design

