7.2.5 Analysis Visit Windows

According to Section 4.3 of the protocol, the analysis visit windows for efficacy analyses will be defined. Analysis windows for the secondary endpoint will be defined within the OP and LT_T analysis periods that are defined in Section 7.2.4 (See [Table 2](#)[Table 2](#)). The calculation of number of migraine days will be based on the study day as defined in Section [Error! Reference source not found.](#)[7.2.3](#). Analysis windows for the exploratory endpoints will be defined directly as below in [Table 3](#)[Table 3](#).

Table 2. Analysis Windows for Migraine Days

Per 4-week Interval	Analysis Window in the LT _T Analysis Period (Study Day)
Month 1: Week 1 to Week 4	1-28

Month 2: Week 5 to Week 8	29-56
Month 3: Week 9 to Week 12	57-84
Month 4: Week 13 to Week 16	85-112
Month 5: Week 17 to Week 20	113-140
Month 6: Week 21 to Week 24	141-168
Month 7: Week 25 to Week 28	169-196
Month 8: Week 29 to Week 32	197-224
Month 9: Week 33 to Week 36	225-252
Month 10: Week 37 to Week 40	253-280
Month 11: Week 41 to Week 44	281-308
Month 12: Week 45 to Week 48	309-336
Month 13: Week 49 to Week 52	337-end of LTT

Table 3. Analysis Windows for MSQoLQ, MIDAS, PoM, SM, and CGI-c Scale

Scheduled Visits *	Target Day (Based on Study Day)	Analysis Window (Study Day)
Baseline	1	Prior to or on the first dose date
Week 12	84	71-98 #
Week 28	196	183-210 #
Week 40	280	267-294 #
Week 52	364	351- end of LTT
Early Termination	The Early Termination Visit or last post-baseline questionnaire from the early terminated participants	

* The PoM, SM, and CGI-c scale will not be collected at baseline, Week 12 and Week 40.

For early terminated participants, the Week X window end date will be the minimum of (1) Early Termination Date -1 day or (2) Week X analysis window end date, where X is the last Week with Target Day being prior to Early Termination Date.

In [Error! Reference source not found.](#)[Table 3](#), if there are multiple non-missing values fall into a same analysis windows, then the following algorithm will be taken to identify the value for analysis:

1. The value closest to the target day for the visit will be used.
2. If the observations are with equal distance from the target day in absolute value, the one with correct nominal visit label will be used. For example, if two observations fall into the analysis window for Week 28 Visit on Study Days 190 and 202, respectively, the observation that is recorded as Week 28 will be used.

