PoM is a 5-item rating scale used to record participants' perception of whether the study drug they are taking is more beneficial in treating their pain compared with prior medication. The statistical analysis will be based on 3 categories, as shown in the figure below:

Item	Category
I feel much better, and I prefer this drug	Preference for study drug
Slightly better than the prior medication	Preference for study drug
Basically the same as the prior medication	No preference
Slightly worse than the prior medication	Preference for prior medication
I feel much worse, and I prefer my prior medication	Preference for prior medication

The number and percentage of participants in each category will be summarized by visit. The calculation of percentage will be based on participants with PoM data by visit, and the two-sided exact Clopper-Pearson 95% CI will be calculated as described in Section 7.1.

A listing of Preference of Medication (PoM)- will be provided.

Satisfaction with Medication Questionnaire (SM)

The SM questionnaire is a 7-item rating scale used to record whether participants are satisfied with their headache medication. The number and percentage of participants in each category will be summarized by visit. The calculation of percentage will be based on participants with SM data by visit, and the two-sided exact Clopper-Pearson 95% CI will be calculated as described in Section 7.1.

A ~~listing~~ listing of Satisfaction with Medication (SM) Survey will be provided.

Migraine Disability Assessment Questionnaire (MIDAS)

The MIDAS questionnaire is a retrospective participant self-report scale consisting of 5 questions, which is used to measure disability related to headache, such as time lost due to headache caused by paid work or school, housework, and non-working activities. The value and change from baseline in the total score will be presented by visit, with n, mean, SD, maximum, minimum, median and 95% CI as described in Section 7.1.

The total score is calculated as the sum of item scores to all 5 questions.

A listing of individual item score, and the calculated total score will be provided.

Clinical Global Impression-change (CGI-c) scale

The CGI-c scale is a 7-item observer-rated scale used to assess the global improvement in

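### Protocol 6.5.5 gives the investigator's other patients as the only reference for CGI-c; neither document names the participant's own pre-treatment condition

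*Protocol*

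**What the plan says.** Protocol 6.5.5 describes CGI-c in one sentence: it is an observer rating that "rates participant total improvement relative to the investigator's past experience with other participants with the same diagnosis". The section cites reference 9.

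The exploratory objective in Protocol 3.1.3 reads "To evaluate the effect of 75 mg rimegepant ODT treatment on the CGI-c scale". The endpoint in Protocol 3.2.3 is "Percentage of participants in each of 7 categories of the CGI-c scale after treatment with 75 mg rimegepant ODT". SAP 2.3 gives the scale's full name, which includes the word change, and SAP 7.4.2 says "The CGI-c scale is a 7-item observer-rated scale used to assess the global improvement in" participants. Under Protocol 10.5.4 and SAP 7.4.2, the number and percentage in each category are summarised by visit with exact Clopper-Pearson 95% intervals.

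On timing, Protocol 4.3.2 schedules the scale at Weeks 28 and 52 or early termination. The note under Table 3 in SAP 7.2.5 states: "The PoM, SM, and CGI-c scale will not be collected at baseline, Week 12 and Week 40". The Synopsis says CGI-c is completed on paper at the site. Neither document reproduces the form or the wording of its seven categories.

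**The concern.** A rating of change needs a stated starting point. In a single-arm trial, the natural one is the participant's own state before treatment, because there is no control group to supply another. Protocol 6.5.5 instead ties improvement to other patients the investigator has seen. That group is not recorded and differs from one investigator to the next.

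If raters follow the sentence literally, CGI-c shows how a participant fares compared with the rater's other patients, and not whether the participant is better than before rimegepant. If some raters do this and others use baseline out of habit, the percentages pool answers to two different questions. The Clopper-Pearson interval would not reveal this: it expresses binomial sampling error and takes the meaning of each category as fixed.

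**Working it through.** No arithmetic applies. The sample-size and precision figures in Protocol 10.2 and SAP 3.4 rest on migraine days and adverse event rates, and no stated figure depends on the CGI-c reference point. The check is a side-by-side reading of the places where each exploratory scale is defined.

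**Step 1. Reference point stated for each exploratory scale**

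| Scale | Reference point in the documents | Where |
|---|---|---|
| MSQoLQ | Baseline | Protocol 3.1.3, 3.2.3; SAP 2.3, 4.3 |
| MIDAS | Baseline | Protocol 3.1.3, 3.2.3; SAP 2.3, 4.3 |
| PoM | Previous medication | Protocol 6.5.2; SAP 7.4.2 |
| SM | None stated; it records satisfaction with the medication | Protocol 6.5.3; SAP 7.4.2 |
| CGI-c | The investigator's experience of other patients | Protocol 6.5.5 only |

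The contrast shows in adjacent bullets of Protocol 3.1.3. The MIDAS objective is "To evaluate the effect of 75 mg rimegepant ODT treatment compared to baseline on the MIDAS", while the CGI-c objective has no baseline phrase. So the plan states an anchor where it intends one, and the only anchor it gives CGI-c is external to the participant.

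**Step 2. Does another section supply the participant's own baseline?** The Synopsis, Protocol 3.1.3, 3.2.3, 4.1, Table 1, 4.3.2 and 10.5.4, and SAP 2.3, 4.3, 7.2.5 and 7.4.2 all mention CGI-c. None names the participant's pre-treatment condition as the reference. SAP 7.4.2 speaks of global improvement without saying since when.

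**Step 3. Does the citation settle it?** No. In the protocol's reference list, reference 9 is the MIDAS paper, which 6.5.4 also cites for MIDAS. Reference 10 is the psychopharmacology assessment manual, and 6.5.5 does not cite it. A reader who follows the citation arrives at a paper on a different instrument.

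**Step 4. What follows from a literal reading?** Take a participant who is better than before treatment by about as much as the rater's usual migraine patient.

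- Against the participant's own baseline, the rating is improved.
- Against the rater's other patients, the participant does not stand out as improved.

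The two references can also diverge the other way. A participant who is unchanged may compare well if the rater's other patients tended to worsen. The documents establish that the two readings can differ. They do not show how often or by how much, and without the category wording one cannot say which category such a participant would receive.

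**The case against.** The strongest reply is that 6.5.5 is a short description of a scale and not a rating manual. Raters work from a paper form that the documents do not show. The same sentence speaks of the participant's total improvement, which already implies comparison with an earlier state. Past experience with other patients can then be read as the yardstick for judging how large that improvement is. This reading is reasonable and cannot be excluded. It limits the point to what the text states and leaves the actual ratings open. It does not remove the point: the sentence sits in the study-procedures chapter, its grammar ties improvement to other patients, and nothing else in either document names the starting point.

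A reader might also infer two stronger things that the documents do not support.

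- **That the CGI-c percentages do not measure change on rimegepant.** This would require the form or the rater instructions, and no passage tells raters to disregard the participant's own earlier condition.
- **That the missing baseline CGI-c rating is itself a defect.** It is not. A change rating is given directly at follow-up, and PoM and SM have no baseline assessment either.

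Nor can the shift be sized from the migraine-day figures in Protocol 10.2. Those are Weeks 9-12 results from another study on a different measure, and the improvement of the rater's other patients would have to be invented.

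It is also fair to say that neither document labels the CGI-c percentages as change from baseline, and that rewriting 6.5.5 without looking at the form could put the protocol at odds with the instrument in use. The second objection fixes the order of the steps in the remedy.

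**Conclusion.** The point holds as a conflict in the stated reference. Protocol 6.5.5 gives CGI-c an external comparator, neither document gives the participant's own pre-treatment condition, and this does not fit a scale of change that the SAP uses to assess participants' improvement. As written, the percentages and intervals cannot be read with confidence as improvement on treatment.

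No numerical size can be given. The actual effect runs from none, if the form anchors to the participant's own earlier state and raters used it, to a different meaning for the whole table, if raters used the 6.5.5 wording literally. The reach is small in either case. CGI-c is one of five exploratory endpoints, the analysis is descriptive without hypothesis tests, and the safety conclusions, the secondary endpoint, the sample size and the interim analysis do not use it. The correction is worth making because it is cheap and because the ambiguity falls on the meaning of every CGI-c result.

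**What to change.** 1. Check the wording of the paper CGI-c form used at the sites before changing any text.
2. In Protocol 6.5.5 and SAP 7.4.2, state that the investigator rates total change at Weeks 28 and 52/early termination compared with the participant's condition at the Baseline Visit.
3. In 6.5.5, correct the citation from reference 9 (the MIDAS paper) to reference 10 (the assessment manual).
4. If the form carried the other-patients wording, footnote the CGI-c table with the reference that was used and do not interpret those percentages as change from baseline. If the form was clarified part-way, the footnote should say that ratings before and after may rest on different references.

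The cost is one sentence in each document, one corrected citation and a short reminder to sites. No assessments or participants are added. The downside is the possible footnote where ratings were made under different wording.

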### **6.5.6. Demographic Information**

Demographic data including age, date of birth, gender, height, weight, ethnicity, etc. will be collected at the Screening Visit. These data will be recorded in the original records, and the data not involving the participant's personal information or privacy will be recorded in the eCRF.

## **6.6. Early Termination of Treatment**

Participants must discontinue study drug (at the discretion of the investigator) for any of the following reasons:

- Withdrawal of informed consent (participant withdrawal for any reason);
- The investigator considers the participant should be discontinued from investigational product for safety reasons (e.g., the participant develops intolerable adverse events);
- Participant is pregnant;
- The participant experiences a serious protocol deviation, and the investigator considers that the protocol deviation seriously affects the evaluation of primary endpoint of this trial, the investigator considers that the participant should terminate the treatment;
- Other conditions that, in the opinion of the investigator, would make the participant discontinue trial medication.

During the trial, all participants who prematurely discontinue treatment should make every effort to complete subsequent safety visits.

## **6.7. Early Withdrawal Criteria**

Participants who meet the following criteria will be withdrawn from the study:

- Poor participant compliance and inability to comply with the study protocol;
- Participant lost to follow-up;
- The participant withdraws consent and requests withdrawal from the study and subsequent follow-up.

During the trial, the participant may decide to withdraw from the trial treatment and late follow-up for any reason at any time. After the participant decides to withdraw, the investigator should record the information of withdrawal event of the participant, including at least withdrawal date and reason. Lost to follow-up is defined as failure to contact the participant after 3 times of telephone calls or other methods, such as mail/registered mail/express mail. The investigator should record the specific situation of lost to follow-up, including at least the date and way of trying to contact.

## **7. STUDY DRUG MANAGEMENT**

### **7.1. Overview of Study Drug**

#### **7.1.1. Basic Information**

Drug name: Rimegepant;

Code: PF-07899801 (Formerly BHV3000);

Specification: 75 mg;

Dose form: Orally Disintegrating Tablets (ODT);

Submitter: Pfizer Inc.

For additional details, please refer to the study drug instruction manual provided by Pfizer Inc. to the clinical study site.

#### **7.1.2. Packaging, Labeling and Storage**

In accordance with the requirements of GCP and national regulations, the application of the label on the packaging box of investigational drugs will be performed by Pfizer Inc. Investigational drugs will be packaged uniformly for all Participants.

The content of the labels of investigational drugs shall comply with the requirements of GCP and national regulations, and shall only be indicated for clinical trials, clinical trial information and information of investigational drugs. The specific packaging shall be participant to the physical objects.

Investigational medicinal products should be stored under ambient conditions (temperature and light) as specified by the sponsor and in a secure, limited access area.

The medication will be stored in a locked, environmentally controlled, limited access medicine room.

## **7.2. Dosage and Administration**

### **7.2.1. Method of Assigning Participant Numbers**

Participants will be assigned a unique participant number consisting of 5-digit Arabic numerals after signing the informed consent form and prior to relevant study examinations: the first 2 digits will be the "site number" and the last 3 digits will be the "screening serial number". For example, the screening number of the second screener at site 01 is "01002". The participant number will be used to identify the participant throughout the study and the assigned number will not be reused for other participants in the study.

### **7.2.2. Dosage and Administration**

Study drug will be dispensed at the Baseline Visit, and participants will be notified by phone after the site staff confirms that the participant is enrolled. Participants confirmed to be

eligible can start taking the study drug rimegepant 75 mg (up to 1 tablet per day) at the time of their migraine attack (mild, moderate, or severe), and use of the study drug will be recorded with BYOD.

